Eye-movements are continuously sampled at the rate of 500 Hz (every 2 ms) from trial onset to the onset of the pointing prompt. Fixations are coded as present (looks to an area of interest on screen) or missing (looks away from these interest areas, track loss, blinking). Present looks are recoded as Agent fixations or Patient fixations based on the looks' relation to target sentences. "Agent fixations" are looks to areas of interest where first-mentioned noun phrases are agents (i.e., correct interpretation for actives and subject relative clauses). "Patient fixations" are looks to areas of interest where first-mentioned noun phrases are patients (i.e., correct interpretation for passives and object relative clauses). Based on pilot data, linguistically mediated eye-movements in responses to the speech stream occur primarily during a 2-second window from the disambiguating verb morphology. Also, consistent with prior work (Huang et al., 2013; Huang et al., 2017), our pilot data indicate that interpretations of canonical structures (i.e., actives) occur faster than noncanonical structures (i.e., passives). On this basis, we will run separate analyses over an "early window" (e.g., first 1000 ms after disambiguation) and "late window" (e.g., second 1000 ms after disambiguation). To examine sensitivity to the timing of window transitions, and to better pinpoint typical timing of stimulus effects, we will explore a range of time values distinguishing potential early and late windows.

Within these windows, we will first calculate **Agent Preference** for each item and then use this value to derive **Structural Sensitivity** for each set of sentences (active/passive, subject/object relative clause). First, for each test point (pre- and post-) and sentence type, we will determine whether canonical and noncanonical structures elicit different interpretations. **Agent Preference** will be calculated as an averaged proportion of Agent looks over Agent plus Patient looks. Values greater than 0.5 indicate a preference to look at the Agent while values less than 0.5 indicate a preference for the Patient.

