We will also use generalized additive mixed models (GAMMs) to model longitudinal patterns in eyetracking data (i.e., looks to the agent) to examine and visualize timing of stimulus effects and changes in focus at key points during and after presentation of the prompt. GAMMs model fixations as an intensive time series (Cho et al., 2018, 2022) and allow identification of key points of separation. Moreover, the GAMMs models do not require prespecification of windows of time, providing more flexibility and sensitivity when modeling differences in eyetracking over time and between groups. The specification of the GAMMs models will mirror the GLMM equations below, except that smoothing functions will be used for an additional TIME predictor to fit a spline regression for each time series.

Aim 1. Determine the relative differences in the efficacy of illustrated syntax stories and recast therapy when treatment is dose controlled and delivered by highly trained SLPs in the laboratory.

We will first confirm that we achieved control of dose in the two in-lab conditions. We will carry out an unpaired two-tailed t-test comparing the estimated dose delivered for each condition. We anticipate that the two conditions will not differ and that the distributions will show high degrees of overlap ($p>.5$, $d<.3$).

To test the key question in Aim 1, we will compare the relative effect of treatment condition by testing for differences between the treatment effect estimates of stories in the lab and recasts in the lab conditions.

Well-matched groups at pretest will be evident if the two conditions do not differ at pre-test. If one treatment condition is more effective than the other, this should be evidenced by an interaction between test point and treatment contrast effects that are significant at the p<.05 level; if, as we hypothesize, the two conditions are equally effective there will be no significant interaction between test point and treatment. We are powered to detect an effect size difference of .35 (2 raw score points) or larger on production.

$$\begin{aligned} \text{Likelihood of a Correct Production} &= \text{TestPoint} * \text{TreatmentCondition} \\ &\quad + (1|\text{item}) + (\text{clause type} |\text{subject}) \\ \text{Structural Sensitivity} &= \text{TestPoint} * \text{TreatmentCondition} \\ &\quad + (\text{clause type} |\text{subject}) \end{aligned}$$

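### The specification of the eye-tracking GAMMs has no term for within-trial dependence or child-specific change, so p-values and separation points for test-point-by-arm and arm-by-time differences would be strongly anti-conservative

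*Protocol*

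**What the plan says.** Under Data Reduction, Eye-tracking Data, the protocol gives the sampling rate: "Eye-movements are continuously sampled at the rate of 500 Hz (every 2 ms". It adds that language-driven eye movements "occur primarily during a 2-second window from the disambiguating verb morphology". The score analysed for Aims 1 and 2 is Structural Sensitivity, one value per child, structure and test point.

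The GAMMs have a different outcome. Under Analytic Approach they are used "to model longitudinal patterns in eyetracking data (i.e., looks to the agent", and the text says "GAMMs model fixations as an intensive time series". Their purpose is "to examine and visualize timing of stimulus effects and changes in focus at key points". The same paragraph also says that they "allow identification of key points of separation", and that they will model gaze differences between groups and across time without pre-set windows.

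The model is then fixed in one sentence: "The specification of the GAMMs models will mirror the GLMM equations below, except that smoothing functions will be used for an additional TIME predictor". That sentence ends by saying that a spline is fitted for each time series. In the equations under Aims 1 and 2, the random part for comprehension is a subject intercept with a clause-type slope. The production equations add an item intercept. Neither contains a trial term, a child-by-test-point term or a correlated error.

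**The concern.** The mirrored equations suit the data they were written for. With one Structural Sensitivity score per child, structure and test point, there is no series of gaze samples to be correlated, and much of a child's own pre-to-post change falls into the residual, where it counts as error. With many gaze samples per trial, neither holds. Successive samples mostly repeat the same look, and child-specific change is swamped by a residual term that shrinks with the number of samples.

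The terms at risk are those for which the GAMMs are offered: whether arms differ in their change from pre-test to post-test, and when in the sentence their curves separate. A standard error that is several times too small would produce separation points by chance. With no pre-set windows, nothing limits where they appear.

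**Working it through.** **Inputs from the protocol.** Sampling rate 500 Hz; 2-second window; 35 children expected per condition; 48 comprehension items per test point; significance level 0.05.

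**Assumptions.** The protocol gives no dwell time (how long gaze stays on one picture), so a range is used. Tests are taken as two-sided. An even split of the 48 items over four sentence types gives 48/4 = 12 trials per type.

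**Sampling interval.** 1000/500 = 2 ms, as the protocol states. The window therefore holds 2000/2 = 1,000 samples per trial.

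**Design effect.** For a two-state gaze process with mean dwell D and sampling step s (both in ms), the lag-1 correlation is ρ = exp(−2s/D). With T = 2000/s samples per trial, the variance of a trial mean exceeds its independent-sample value by

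DE = (1+ρ)/(1−ρ) − 2ρ(1−ρ^T)/[T(1−ρ)²].

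A nominal 5% test that ignores this rejects with probability 2[1 − Φ(1.96/√DE)]. The number of children does not enter, so a larger trial does not help.

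Example with D = 300 and s = 2: ρ = exp(−4/300) = 0.9868; DE = 150.0 − 11.2 = 138.8; √DE = 11.8; rejection rate 86.8%.

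| Dwell (ms) | Step (ms) | ρ | DE | SE too small by | Rejection rate under no effect |
|---|---|---|---|---|---|
| 200 | 2 | 0.9802 | 95.0 | 9.7 | 84.1% |
| 300 | 2 | 0.9868 | 138.8 | 11.8 | 86.8% |
| 500 | 2 | 0.9920 | 218.8 | 14.8 | 89.5% |
| 800 | 2 | 0.9950 | 320.5 | 17.9 | 91.3% |
| 300 | 20 | 0.8752 | 13.9 | 3.7 | 59.9% |
| 300 | 50 | 0.7165 | 5.6 | 2.4 | 40.8% |

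At 150 ms dwell and 2 ms spacing, the leading term alone gives DE = 75 and a rejection rate of 82%. At 50 ms spacing, the rate runs from 32% (dwell 200 ms) to 58% (dwell 800 ms).

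**Simulation under no treatment effect.** 35 children per arm, two test points, two clause types with 12 trials each, child-by-clause effects removed, and a polynomial with 5 degrees of freedom in place of the TIME smooth. There were 150 runs per setting at 2 ms and 400 at 20 and 50 ms.

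| Test, ignoring serial dependence | 2 ms, dwell 300 | 2 ms, dwell 500 | 20 ms, dwell 300 | 50 ms, dwell 300 |
|---|---|---|---|---|
| Test point by arm | 86% | 93% | 64% | 39% |
| Arm by TIME curve | 100% | 100% | 92% | 68% |

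**What repairs it.** At 2 ms, with between-child variation as the error term, both tests rejected 5.3% of the time at either dwell. An AR(1) correction alone gave 6-7% for test point by arm when children did not differ in pre-post change. It gave 35% when they did (assumed SD 0.10 on the looking proportion, 100 runs). The arm main effect, tested between children, stayed at about 5-6% at 2 ms.

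**The case against.** The strongest objection is that the text is less definite than a literal reading makes it. A spline for each time series could mean a smooth per child or per trial, and with such terms the false-positive rate would fall to near nominal. The Analytic Approach also allows random slopes as a possibility, so the equations may not be the full random structure. The description as an intensive time series rests on cited papers that cannot be checked here. These points stand as ambiguity, but they do not settle the matter. The sentence names one exception to mirroring, and the optional slopes are listed for subjects, items and clause type, with no mention of trial, TIME or correlated errors. The sponsor's own Power Analysis for Production includes a child-level random effect for each of the four repeated measures, which lets children differ in their change; the equations to be mirrored do not.

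Three stronger readings are tempting, and the documents do not support them.
- A reader might infer that almost any arm difference would appear significant. The between-child arm main effect would not, because the subject intercept protects it.
- A reader might take it as stated that raw 2 ms samples are the rows of the model. The protocol gives a sampling rate and no binning, so this is an inference. Coarser rows reduce the problem without removing it.
- A reader might conclude that the comprehension findings for Aims 1 and 2 are compromised. Those rules rest on GLMM interactions. The GAMMs are supplementary and have no decision rule of their own.

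It is also fair to say that the simulation is a linear approximation and not a fitted GAMM.

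**Conclusion.** The concern holds for a limited set of results. Under the specification as written, GAMM p-values and separation points for test-point-by-arm and arm-by-time differences would be strongly anti-conservative. False-positive rates for test point by arm are roughly 80-90% or more at 2 ms for dwell times of 150 to 500 ms, and about 40% at 50 ms with 300 ms dwell; the arm-by-time curve fares worse. These figures rest on assumed dwell times, a two-state gaze process, and a reading in which no per-child or per-trial smooth is fitted. The direction does not depend on the exact dwell time; the size depends on the row spacing, which the protocol does not give.

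This is more than detail that could be left for later: the protocol's update note says that it includes the statistical analysis plan, and the paragraph fixes a model that is wrong for this outcome. The primary conclusions for Aims 1 and 2 are not at stake, so the change is advisable and does not threaten the trial's validity.

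**What to change.** Replace the statement that the GAMMs mirror the GLMM equations with a specification of their own. It should:
- state the time bin that forms a row of the data;
- include random smooths of time per child by test point and clause type;
- handle the remaining within-trial dependence by a trial effect, AR(1) errors, or both.

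An AR term alone is not enough, because it leaves out differences between children in pre-post change. Alternatively, label the GAMMs descriptive and report fitted curves with no p-values and no significance-based separation points.

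The cost is a change of wording, longer model fitting and wider intervals than the written model would give. No new data are needed.

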****Updated to add changes in inclusionary criteria**

****Updated July 15, 2025 – Includes statistical analysis plan.**

Human Subjects Involvement, Characteristics, and Design

The study is a Phase I clinical trial that employs a randomized parallel design. We plan to enroll 160 children diagnosed with Developmental Language Disorder and their caregivers who will provide services to approximately half of these children. We predict that 15% of the children (N=20) will be lost to follow-up, thus we enroll 160, in order to have 140 children complete the entire study and meet the planned enrollment goals. Children will be randomly assigned to one of four treatment conditions, thus we expect 35 participants per condition. Research will be carried out at the University of Delaware and the University of Maryland College Park.

Children with Developmental Language Disorder (N = 160)

Inclusionary & Exclusionary Criteria:

- Age: 4-7 years old
- Primarily English speaking: Less than 20% exposure to another language, per parent report
- Document poor syntax skills: standard score below 85 on the DELV-NR composite, a dialect neutral assessment (Seymour, Roeper, de Villiers, & De Villiers, 2005).
- Nonverbal IQ within typical range: t-score at or above 35 on the DAS, matrices subscale, (Elliott, 2007).
- Hearing within the typical range: Pass screening using SoundScouts (Gumbie et al., 2018; Mealings et al., 2020) or provide reports of passing a hearing screening at school or in a pediatrician's office. *Due to COVID and limitations on in person activities, treatment may proceed even if these reports are not obtained if no one has concerns about hearing and we will track/follow up with families to obtain a clear hearing screening within 12 months of completion of intervention. Documentation of how many children did not complete hearing screenings will be retained and inform interpretation of data.
- No diagnosis of Autism: Cutoff score of 15 on the SCQ, (Rutter, Bailey, & Lord, 2003)
- No diagnosis of significant sensory-motor concerns or significant psychiatric disorders per parent report
- Able to benefit from treatment:
 - Score below 60% correct on experimenter developed elicited production probes of passives and object relative clauses
 - Producing simple transitive sentences (SVO) and MLU of 2.5 on 100 utterance language sample

Caregivers of Children with DLD (N=160)

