In the somewhat likely event that the interaction between time point and treatment is not significant, we can directly test for treatment efficacy by comparing the effect of treatment on the treated vs. untreated structures. We expect that the model estimate for Treated or Untreated clause will be significant at p<0.05 level, favoring the treated clauses, demonstrating that treatment was effective and ruling out maturational effects.

$$\begin{aligned} \text{Likelihood of a Correct Production} &= \text{TestPoint} * \text{TreatedOrUntreated} \\ &\quad + (1|\text{item}) + (\text{clause type} |\text{subject}) \\ \text{Structural Sensitivity} &= \text{TestPoint} * \text{TreatedOrUntreated} \\ &\quad + (\text{clause type} |\text{subject}) \end{aligned}$$

Aim 2. Determine whether the influence of delivery method (illustrated syntax stories or recast therapy) on dose delivered (number of exposures to the target) is of sufficient magnitude that changes in child outcomes are observed when treatment is delivered by caregivers.

We will first determine whether dose differs across the two at-home conditions. We will carry out an unpaired two-tailed t-test comparing the estimated dose delivered for each condition. We anticipate that the two conditions will differ and that the distributions will show low degrees of overlap (p<.05, d>.5).

To test the key question in Aim 2, we will test for a dose by test point or dose by treatment condition by test point interaction for stories at home and recasts at home conditions. Well-matched groups at pretest will be evident if the two conditions do not differ at pre-test. If one treatment condition is more effective than the other, this should be evidenced by an interaction between test point and treatment contrast effects that are significant at the p<.05 level; if, as we hypothesize, dose is a critical component of this difference, a two- or three-way interaction between time and dose or between time, treatment and dose will be observed. We would interpret the two-way interaction as indicating that dose, rather than treatment is critical for obtaining the key outcomes. A three- way interaction suggests that the delivery method modifies the effectiveness of the total dose.

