$$\begin{aligned} \text{Likelihood of a Correct Production} &= \text{TestPoint} * \text{TreatmentCondition} * \text{EstimatedDose} \\ &\quad + (1|\text{item}) + (\text{clause type} |\text{subject}) \\ \text{Structural Sensitivity} &= \text{TestPoint} * \text{TreatmentCondition} * \text{EstimatedDose} \\ &\quad + (\text{clause type} |\text{subject}) \end{aligned}$$

In the event that the interaction between time point and treatment is not significant, we can directly test for treatment efficacy by comparing the effect of treatment on the treated or untreated structures. We expect that the model estimate for Treated vs. Untreated clause will be significant at p<0.05 level, favoring the treated clauses, demonstrating that treatment was effective and ruling out maturational effects.

$$\begin{aligned} \text{Likelihood of a Correct Production} &= \text{TestPoint} * \text{TreatedOrUntreated} \\ &\quad + (1|\text{item}) + (\text{clause type} |\text{subject}) \\ \text{Structural Sensitivity} &= \text{TestPoint} * \text{TreatedOrUntreated} \\ &\quad + (\text{clause type} |\text{subject}) \end{aligned}$$

Power Analysis for Production

Power analyses were carried out using Monte Carlo simulation (5,000 iterations) via SAS 9.4 and PROC GLIMMIX using residual pseudolikelihood estimation of a binary logistic mixed effects model with item responses (n=20) nested within tests (n=4 representing test point and clause type repeated measures) that are nested within children (n=120) who have been randomly assigned to treatment conditions, counterbalanced across the 2 clauses. Random effects are included for items within clauses, as well as four correlated child-level random effects (i.e., for each of the four repeated measures). A single model was used to estimate power in alignment with the overall design of the study in which children are randomly assigned to one of FOUR conditions. Power for the more focused models described above can be inferred from the power estimates for the treatment contrasts below. By adopting this randomization scheme and model design, we retain the ability to test unplanned contrasts that go beyond the planned analyses for the Aims if we so chose (e.g., recasts in the lab vs. recasts at home) in order to carry out secondary analysis associated with cost effectiveness, dose, or home environment.

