The influence of dose (Aim 2) was simulated by predicting different dose distributions for each condition. These distributions were simulated and then we randomly sampled from the distribution for each case. Hypothesized distributions of dose lead to substantial changes in the result, and thus we make our method of construction these distributions clear here. We assume that a minimum dose is achieved during the training visits (home condition) or by attending at least 1 session (lab condition) for all children. The two in-lab conditions are highly similar and both assume that 25% of participants attend between 1 and 12 sessions, 25% attend between 12 and 16, and the remainder have perfect attendance. This is a conservative estimate based on attendance data from our summer camp study.

The two at-home conditions require slightly more explanation. We assume for recasts that the first quartile has a dose of up to 1 recast/5 min for 60 min per week. The next quartile extends up to 1 recast/5 min for 120 min per week. The third quartile ranges up to a dose of 1 recast every 3 min for 120 min per week and the last quartile assumes target delivery. Similarly, syntax stories at home escalates from reading 1x/week to reading 2x/week to reading 4x/week (as asked) to reading 1 syntax story daily as the maximum. Several families in the pilot data for the syntax stories read the provided syntax stories daily.

Table 1. Hypothesized dose delivered by condition, in quartiles

	Recasts in lab	Stories in lab	Recasts at home	Stories at home
minimum	60	60	60	60
1st quartile	768	768	96	240
median	912	930	192	460
3rd quartile	960	960	320	960
maximum	1008	960	960	1680

Next the gain obtained from each dose was estimated by multiplying the dose provided by a value drawn from a uniform distribution ranging from .0005 to .006, to account for the fact that some children will be more responsive to any given dose than others. Finally, the gain was added to the pretest scores to yield posttest values. Simulations were checked to ensure that final post-test means and standard deviations for the treated structure were in line with estimates for post-test gains used for Aim 1 simulations. Planned statistical analysis were carried out over the simulated data and these simulations were repeated 1000 times.

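### A t-test with p>.5 cannot confirm that the two lab arms received equal dose: with identical true doses that mark is missed half the time at any sample size

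*Protocol*

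**What the plan says.** Protocol, Analytic Approach, Aim 1: "We will first confirm that we achieved control of dose in the two in-lab conditions". The method is "We will carry out an unpaired two-tailed t-test comparing the estimated dose delivered for each condition". The anticipated result is no difference, and that "the distributions will show high degrees of overlap ($p>.5$, $d<.3". These are the only marks given for dose control. No margin or confidence interval for the dose difference is stated, and nothing is said about what follows if the marks are missed. The Aim 1 outcome models contain test point and treatment condition but no dose term.

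Aim 2 uses the same test for the two at-home arms and anticipates that "the distributions will show low degrees of overlap (p<.05, d>.5". There, estimated dose is a term in the outcome models.

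The Power Analysis for Production section gives assumed dose distributions ("Table 1. Hypothesized dose delivered by condition, in quartiles") and says of the lab arms: "The two in-lab conditions are highly similar". On numbers, the opening design section says "thus we expect 35 participants per condition". The power simulation uses item responses within tests "that are nested within children (n=120", which is 30 per arm over four conditions.

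**The concern.** Aim 1 asks how the two treatments compare when dose is controlled. Its outcome model does not adjust for dose, and Aim 2 hypothesises that dose matters. The equal-dose reading of the lab contrast therefore rests on the 960-exposure target set for both treatments and on this check of what was delivered.

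A significance test of no difference is the wrong instrument for that purpose. A large p-value is not evidence of equality, and asking for p>.5 makes lab arms with truly equal dose miss the stated pattern half the time. What is at stake is interpretation. A well-matched lab comparison could be reported as falling short of the plan's own expectation. If the mark is relaxed to the usual .05, arms that differ by a material amount could be reported as having confirmed dose control.

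**Working it through.** The protocol gives no pass rate or overlap percentage for these marks, so there is no figure to reproduce. The steps below work out how the marks behave.

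**Inputs.** n = 35 per arm (opening design section), with 30 per arm (120/4, power section) as a sensitivity case. The marks are p>.5 with d<.3 (Aim 1) and d>.5 (Aim 2). Dose quartiles come from Table 1. Assumption: doses are spread evenly between adjacent quartiles.

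**Lab dose implied by Table 1.**
- Recasts in lab, interval midpoints 414, 840, 936, 984: mean = 3174/4 = 793.5, SD about 248.
- Stories in lab, midpoints 414, 849, 945, 960: mean = 3168/4 = 792, SD about 246.
- The difference is about 1.5 exposures (d about .006), so the plan's own assumption is essentially equal dose. An SD of 247 is used below.

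**How often p>.5 occurs with equal dose.** Under no true difference p is uniform on (0,1), so P(p>.5) = .50 at any n. In 20,000 simulated trials from the Table 1 lab distributions, both marks were met in 50% (n=30), 49% (n=35) and 50% (n=40).

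**Relation between the two Aim 1 marks.** |d| at a given p is t × √(2/n).
- n=35: √(2/35) = .239 and t(.75; 68 df) = .678, so p=.5 is |d| = .162.
- n=30: p=.5 is |d| = .175.
- Conversely, d=.3 at n=35 gives t = .3/.239 = 1.255 and p = .21 (p = .25 at n=30).

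Every result with p>.5 therefore satisfies d<.3, and the d mark never binds. Used alone with equal doses, |d|<.3 would be met 79% of the time at n=35 and 75% at n=30.

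**If p>.05 was intended.** At n=35, p=.05 is |d| = .477. With a true d of .3, the noncentral t distribution gives P(p>.05) = .76 (.79 at n=30). A real difference of .3 SD, or .3 × 247 = about 74 exposures, would usually pass.

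**What 35 per arm can show.**
- 95% half-width = t(.975; 68 df) × √(2/35) = 1.995 × .239 = .477 SD; .477 × 247 = about 118 exposures, or 12% of the 960 target.
- At 30 per arm it is .517 SD, or about 128 exposures.
- The narrower 90% interval used in an equivalence test has a half-width of about 98 exposures (about .40 SD) at n=35, still above .3 SD. Power to show equivalence when the true difference is zero is about 0% at a margin of .3 SD, 34% at .5 SD and 91% at .8 SD.

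**Aim 2 wording.** For normal doses with equal SD, overlap = 2Φ(−d/2): 88% at d=.3 and 80% at d=.5. On the alternative definition (1 minus Cohen's U1) these are 79% and 67%. Table 1 for the home arms implies d of about .96 and overlap of about 59%. Doses in Table 1 are skewed and the home SDs unequal (about 238 and 464), so the normal-theory figures are illustrative. Indeed, counted in 10-exposure bins, the two lab distributions in Table 1 overlap only about 71% despite almost equal means.

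**The case against.** The strongest reply is that the marks are predictions. Both aims word them as what is anticipated, no gate is attached, and the outcome models are run whatever the t-test shows. That stands. A reader might infer that a coin flip decides whether Aim 1 is analysed or accepted, but the protocol says nothing of the kind. What remains is that the sentence introducing the test says it will confirm dose control, and these are the only marks offered for doing so.

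A reader might also infer that p>.5 and d<.3 contradict each other. They do not: the former implies the latter, so the d mark is redundant. A mismatch arises only if p>.05 is substituted, which is not what is printed.

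On Aim 2, d>.5 is a floor. It sits close to what p<.05 already requires (|d|>.477 at 35 per arm), and Table 1's d of about .96 satisfies it. Because dose enters the Aim 2 model directly, the label has no analytic effect. This reply also stands and leaves only a wording point.

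Finally, replacing the check with a requirement that the confidence interval lie within .3 SD would be no improvement: at 35 per arm it would fail even with an observed difference of zero.

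**Conclusion.** The concern holds as a defect in the Aim 1 dose check. The p>.5 mark is missed 50% of the time when doses are truly equal, and no sample size changes that. The printed d<.3 mark adds nothing to it, and p>.05 would pass a true difference of .3 SD about three times in four. Neither version can support a statement that dose control was confirmed.

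The reach is limited. The Aim 1 outcome test and the Aim 2 models do not depend on this check; what is affected is the reading of the lab contrast as treatment type at equal dose. The 50% needs only equal true means and the usual t-test conditions, and the skewed Table 1 distributions reproduce it. The figures in exposures rest on the interpolated SD of about 247 and on 35 completers per arm. The 80% and 88% overlap figures rest on normal doses with equal SD.

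**What to change.** In Aim 1, delete p>.5 and do not treat a non-significant t-test as confirmation of dose control. Report mean exposures in each lab arm and their difference with a confidence interval in exposures, read against a margin in exposures that the investigators justify before the dose data are examined. State alongside it that at 35 per arm the expected 95% half-width is about 118 exposures (.48 SD), so that a margin of .3 SD is not chosen in the belief that it can be met.

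In Aim 2, drop the low-overlap label and report the observed dose difference and the observed overlap.

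The cost is a few sentences and one justified margin, with no new data and no change to the outcome models. The downside is that the report may have to say that close dose equality was not demonstrated.
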